**Aspiration of Gastric Residual Contents**

**NCT 01863043**

**3/4/2016**

## Protocol

**Research Design.** A randomized clinical trial will be conducted to determine the benefits of omitting aspiration of residual gastric contents (RGC) prior to feedings on nutritional outcomes and gastrointestinal integrity and functioning of premature, very low birth weight (VLBW) infants. VLBW infants will be randomly assigned to one of two groups. Group 1 will receive standard care; that is, physical parameters of feeding intolerance and NEC will be assessed and RGC will be aspirated prior to each feeding. In Group 2, physical parameters for feeding intolerance and NEC will be assessed but RGC will not be aspirated. To determine nutritional outcomes, the following factors will be evaluated: (1) weekly enteral intake for the first 6 weeks of life, (2) time to reach full enteral feedings, (3) hours of parenteral nutrition (PN), (4) diagnosis of parenteral nutrition associated liver disease (PNALD), (5) growth indices, (6) hours of central venous line (CVL) access, (7) episodes of late onset sepsis (LOS), (8) length of hospital stay. The presence of gastrointestinal bleeding and inflammation will be measured by (1) presence of blood in the stool, and (2) fecal calprotectin levels. Furthermore, plasma levels of gastrointestinal peptides including serum gastrin and motilin will be measured as indicators of gastrointestinal function. See Table 1.

**Sample and Setting.** The proposed study will follow a prospective cohort ( $N = 120$ ) of racially and economically diverse VLBW infants for 6 weeks following birth. The infants will be born to mothers who are English or Spanish speaking and who are 18 years of age or older. VLBW infants will be sampled by convenience from the neonatal intensive care unit (NICU) at Shands Children's Hospital, a Level III tertiary care center. The hospital is part of the University of Florida and includes a 52 bed NICU. The hospital catchment area encompasses north central Florida and southern Georgia, a predominantly rural and semi-rural population. Approximately 100-110 VLBW infants are delivered there per year. In the preliminary study, 70% of mothers consented for the study. Inclusion criteria for the infants are as follows: (1) born at 32 weeks or less of gestational age, (2) birth weight equal to or less than 1,250 grams, and (3) infant receiving some enteral feedings by 72 hours of age and parenteral feedings by 24 hours of age. Exclusion criteria for the infants are as follows: (1) congenital or chromosomal abnormalities, (2) complex congenital heart diseases and congenital anatomic gastrointestinal abnormalities, (3) Infants will be withdrawn from the study if any of the following occur: grossly bloody stools, radiologic evidence of NEC, or other intestinal complications such as perforation.

**Sample Size Determination / Power Analysis.** In the preliminary study, 40 premature, VLBW infants had a mean enteral intake at 14 days of 72 mL/kg/d ( $SD=65$ ). To detect a 50% improvement to 108, we would require 104 evaluable subjects in a non-sequential design for Primary 1.1 to achieve 80% power at  $P=0.05$  (two-sided). To accommodate one interim analysis, we employed the minimax method of Shuster et al (2002), with first look after 66 evaluable subjects have been accrued. If  $|Z|>2.28$  we shall stop for significance. If  $|Z|<1.12$ , the study will be reviewed for possible futility. There will be no stopping for futility. Otherwise, the study will accrue 120 evaluable subjects (54 more). No competing two stage design can achieve a lower worst case scenario average sample size than this one's 89 evaluable. Intent-to-treat will be followed as closely as possible. However, to accommodate dropouts including deaths (15%) and infants who develop NEC (7%) we expect to accrue 160 subjects.

**Randomization.** Within 72 hours of life and within 24 hour of initiating feeds of less than 20 mL/kg/d, informed consent will be obtained from the mothers, and infants will be randomly assigned to one of two groups by random length permuted blocks of sizes 4, 6, or 8 to maintain approximate balance assigned to each treatment group.

**Standard Infant Feeding Protocol.** As per standard NICU protocol, all infants will begin receiving PN within 24 hours of life. In addition, all infants will have an orogastric (OG) or nasogastric (NG) tube placed upon admission to the NICU and begin receiving enteral feeding of less than 20 ml/kg/d within 72 hours. Length of insertion of the OG/NG tube is determined by measuring from the tip of the nose to the tip of the ear lobe and then halfway between the xiphoid process and umbilicus (Ellett et al., 2011). Minimum insertion length based on the weight of the infant (Cordero et al., 2011). If the infant receives an X-ray upon admission, placement of the OG/NG tube is verified. Placement is also verified if additional X-rays are taken during the study as per usual OG/NG placement protocol in the NICU. Depending on the infant's gestational age, weight, and clinical status, feedings are initiated at up to 20mL/kg/d and advanced daily by no more than 20mL/kg/d toward a goal of 120-150mL/kg/d divided into 8 equal feedings per day using the established University of Florida Children's Hospital NICU feeding guidelines. Mom's own breast milk is encouraged, and donor breast milk provided if mothers own breast milk is unavailable. Prior to each feeding, the OG/NG tube is checked for proper placement by the bedside nurse verifying the insertion length with the initial measured insertion length. In addition, the nurse assesses the infant for any signs or symptoms of feeding intolerance or NEC (i.e., abdominal distension and/or tenderness, increased abdominal girth, visible bowel loops, presence of emesis, and visible blood in the stool). It is standard protocol to aspirate RGC prior to each feeding. However, for this study, this will only occur in infants randomized to Group 1. Kangaroo Care (holding of an infant dressed only in a diaper upon someone's bare chest) can positively affect growth and improve feeding tolerance (Conde-Aquedelo et al., 2011) Kangaroo care is encouraged in this NICU and nursing protocols have been established to provide support to all mothers regarding provision of kangaroo care.

**Research Procedure.** The procedures used in this study will be the same as those successfully used in the preliminary study. Following consent by the mothers, infants will be randomized, and baseline demographic data will be collected from their medical charts. Over the first 6 weeks of life the following additional information will be collected at specified time periods from their medical charts: weekly enteral intake, days to full enteral feedings (120 mL/kg/d), hours of PN, evidence of PNALD (level of direct bilirubin, alkaline phosphatase, aspartate aminotransferase (AST) and alanine aminotransferase (ALT)), growth indices (weekly weight, head circumference and length), medications, hours with a CVL, episodes of presumed or culture proven LOS (occurring > 7 days of life), days to discharge, evidence of stage 2 or greater NEC, evidence of aspiration pneumonia on chest radiograph, episodes of ventilator associated pneumonia and guaic status of stools. Additionally, one stool sample will be collected at 3 and 6 weeks to test for fecal calprotectin levels. 1mL of blood will be collected during a routine blood draw between 7 and 14 days of life to test for serum gastrin and motilin levels. If ventilated, tracheal aspirate samples will be collected on days 1, 3, 5, 7, 14, 21, 28 and 35 from routine tracheal aspirate suctioning. As kangaroo care is a potentially confounding factor, episodes and duration of kangaroo care between mother and infant will be recorded on the Kangaroo Care log sheet located at the infant's bedside by either the mother or the nurse. See Table 1.

**Aim 1.** The primary aim of this study is to determine the risks and benefits of aspirating RGC and the clinical benefits of omitting aspiration of RGC prior to enteral feedings on the nutritional outcomes of premature VLBW infants. Both groups will have a sign placed on their isolettes stating which group they are assigned to and whether the nurse should or should not aspirate RGC. Although already documented on the infant's flow sheet, the sign will also include an area for the nurse to document the OG/NG insertion depth. Those personnel who are not involved with the study infants will be unable to be blinded since information regarding gastric residual volume and color is placed in the chart by the nursing staff and monitored by clinicians making decisions regarding enteral feeding plans. The PI is a neonatal nurse practitioner in the NICU

and will not be involved in the feeding plans for any subject in the study. The nurses at this research institution were willing to comply with the protocol in the past and have agreed to do so again. During the pilot study there were no known protocol deviations involving nursing staff. The only difference in care is that the infants in Group 1 will continue to have RGC aspirated prior to each feeding, and Group 2 will not have RGC aspirated. RGC are obtained by gentle aspiration of gastric contents from the indwelling OG/NG tube into a syringe. Decisions regarding advancement of feedings will be made according to the University of Florida Children's Hospital NICU feeding guidelines, including consideration of the physical assessment for signs and symptoms of feeding intolerance and NEC. Data to be collected for Aim 1 are found in Tables 1 and 2.

**Aim 2.** Aim 2 will determine the effect of routine RGC aspiration on gastrointestinal bleeding and inflammation. All stools will be tested for blood by the bedside nurse for the first 6 weeks using point of care guiac test kits, with the results recorded on the infant's flow sheet. Subsequently, this information will be collected and recorded by the project coordinator. Stool will be collected by the bedside nurse at 3 and 6 weeks of age and placed in a vial which is enclosed in a Ziploc® plastic bag and attached to the infant's isolette. Initial inflammatory changes have been seen in the intestinal tract of infants 4 days after an insult and the decision to test at 3 and 6 weeks was made to allow sufficient time for intestinal inflammation to occur from GRC aspiration (Saarinen et al., 2002). . The vial will be collected by the project coordinator who will take the sample to the co-investigator's ([name], MD) existing research laboratory where the calprotectin level will be analyzed. This lab is currently successfully involved with and is proficient in fecal analysis of calprotectin levels. The results will be collected and recorded by the project coordinator.

**Aim 3.** Aim 3 will determine the effect of routine RGC aspiration on gastrointestinal function as evidenced by gastrointestinal peptide activity. Serum levels of gastrin and motilin will be measured on all infants between 14 and 21 days depending upon the timing of a routine blood draw. Since all GRCs are not discarded, waiting until between 14-21 days will allow adequate time for potentially one or more GRC to be discarded. 1 mL of blood will be taken during a routine blood test. All samples will be sent to the laboratory at Shands Children's Hospital at the University of Florida for testing, and lab values will be extracted and recorded by the project coordinator.

**Statistical Analysis.** Data will be entered into the RedCap system by the research assistant. For the primary hypothesis (P1.1), the total weekly enteral intake will be compared between the two randomized treatment groups via a two-sided Welch-corrected T-test. For sample sizes of this magnitude, the central limit theorem assures us that this is an assumption-free analysis, even if the underlying population variances differ. An interim analysis of P1.1 will also be done as described in the Power Analysis section below. Secondary hypotheses S1.1-S1.7 will be tested in the same manner as the primary hypothesis P1.1. For secondary Hypothesis S2.1 (S3.1), [S3.2], we shall compare the personal fractions of positive stools (gastrin levels) [motilin levels] respectively via two-sided Welch-corrected T-tests. For secondary hypothesis S2.2, we shall use a repeated measures analysis of variance to compare the groups with respect to week 3 and week 6 calprotectin levels. . Actual P-values will be reported, and each hypothesis will be accompanied by a point estimate and 95% confidence interval estimate for effect size. For descriptive purposes, a P-value of under 5% will be declared significant. The study is powered strictly around the primary hypothesis P1.1. Withdrawal rates will be compared between the treatments in a tertiary manner using survival analysis (time to withdrawal), via a logrank test.

**Expected outcomes.** Based on the preliminary study, it is reasonable to expect that infants who do not receive routine aspiration of RGC will have better nutritional outcomes, evidence of less gastrointestinal bleeding and inflammation, and improved gastrointestinal function.

**Data Entry and Management.** All data will be entered into a REDCAP database having integrated data quality and consistency checks (e.g., data-range) as part of the data procedure. Data quality will be monitored and assured: 1) as reported; and 2) as entered into the database. For the former, all hardcopy forms will be visually inspected before data entry. Furthermore, a manual comparison of randomly selected data hardcopy forms with data output listing generated from the study database will be performed, and consistency checks will be generated by SQL or SAS programs as part of routine data cleaning procedures. All subjects eligible for enrollment will be registered and entered into the study database designed by the project coordinator.

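### Infants withdrawn after randomization for gut complications have no stated place in the primary analysis, so P1.1 and the interim look can rest on a set selected by post-randomization events

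*Combined protocol and SAP*

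**What the plan says.** The withdrawal rule is printed as the third exclusion criterion under Sample and Setting, but it acts after randomization: "Infants will be withdrawn from the study if any of the following occur: grossly bloody stools, radiologic evidence of NEC, or other intestinal complications".

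Sample Size Determination / Power Analysis counts both looks in evaluable infants. The interim comes "with first look after 66 evaluable subjects have been accrued" and the final analysis at 120. The section then says "Intent-to-treat will be followed as closely as possible", and the next sentence qualifies this: "to accommodate dropouts including deaths (15%) and infants who develop NEC (7%) we expect to accrue 160 subjects". Evaluable is not defined there or elsewhere.

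For P1.1, Statistical Analysis says that "the total weekly enteral intake will be compared between the two randomized treatment groups via a two-sided Welch-corrected T-test". It gives no assigned value, imputation or sensitivity analysis for an infant who was withdrawn or died. The one analysis that concerns withdrawal is this: "Withdrawal rates will be compared between the treatments in a tertiary manner using survival analysis (time to withdrawal), via a logrank test".

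On data sources, Research Procedure says: "Over the first 6 weeks of life the following additional information will be collected at specified time periods from their medical charts". No section says whether abstraction stops when an infant is withdrawn.

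**The concern.** Randomization protects the comparison of everyone randomized. It does not protect a comparison restricted to infants who avoided NEC, gross bleeding and perforation, if the strategy under test can change who has those events. The plan gives reason to think it might: Expected outcomes anticipates less gastrointestinal bleeding when aspiration is omitted, and gross bleeding is a withdrawal trigger. Care is also unblinded, with group signs on the isolettes and residuals charted for the clinicians who set feeding plans (Aim 1).

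The set at risk is not trivial. At the planned allowance, 22% of 160 is about 35 infants, of whom about 11 have NEC. The same gap applies at the interim, where |Z| > 2.28 stops the trial. With no definition of evaluable, the analysis set could also be settled after data have been seen.

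Aim 2 may be affected too. If withdrawal ends collection, later stool tests and the week 3 or week 6 calprotectin sample are lost for the infants in whom they matter most.

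**Working it through.** **Inputs.** From Sample Size Determination / Power Analysis: mean 72 mL/kg/d at 14 days, SD 65, target 108 (difference 36), 80% power, two-sided 0.05, 66 and 120 evaluable, allowances of 15% and 7%, accrual 160. Withdrawal rates by arm and intake in withdrawn infants are not in the documents and are assumed below.

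**The plan's own figure.** n per arm = 2 × (1.960 + 0.842)² × 65² / 36² = 51.2, rounded up to 52, total 104. This reproduces the stated 104. With the t distribution, 104 gives 79.9% power and 106 is needed.

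**Who is evaluable?**
- If infants with NEC counted: 120 / 0.85 = 141.2, so 142.
- If they do not count: 120 / 0.78 = 153.8, so 154.
- Planned: 160. Neither matches exactly, but the second is closer, and an allowance for NEC is unnecessary if those infants stay in.
- At the interim, 66 / 0.78 = 85 to 66 × 160 / 120 = 88 randomized, about 6 of them with NEC.

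**Illustrative shift.** Assume no difference in all-randomized means (72 in both arms), a share p withdrawn with mean intake x, and 60 analysed per arm at a single look. The evaluable mean is (72 − p·x) / (1 − p), and SE = 65 × √(2/60) = 11.87.

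| Loss by arm | x | Evaluable means | Shift | Type I error |
|---|---|---|---|---|
| 10% vs 4% | 0 | 80.0 vs 75.0 | 5.0 | 7.0% |
| 10% vs 4% | 40 | 75.56 vs 73.33 | 2.2 | 5.4% |
| 5% vs 2% | 0 | 75.79 vs 73.47 | 2.3 | 5.4% |
| 5% vs 2% | 40 | 73.68 vs 72.65 | 1.0 | 5.1% |
| 7% vs 7% | same in both arms | equal | 0 | 5.0% |

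The 5% vs 2% rows are the case where half the events fall after day 14 and those infants keep their value.

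**Direction.** At the 5.0 shift (5.0 / 11.87 = 0.42 SE), rejections are 6.2% in the direction of the shift and 0.9% in the other (7.0% in all before rounding). If Group 1 loses more infants, the shift runs against omission of aspiration: the expected difference falls from 36 to 31, and single-look power at 60 per arm falls from about 85% to 74%.

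**A null with no shift.** If event-free infants average 72 in both arms and withdrawn infants take nothing, the evaluable means are equal. The all-randomized means then differ: 72 × 0.90 = 64.8 against 72 × 0.96 = 69.1.

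**Interim.** With 33 per arm, SE = 65 × √(2/33) = 16.0. Under equal all-randomized means, the chance of |Z| > 2.28 is 2.3% with no shift, 2.4% at a shift of 2.2 and 2.9% at 5.0.

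**Effect of analysing everyone.** Here 72 and 108 are taken as event-free means, with a share q of each arm at zero intake. The difference is 36(1 − q), and each arm's SD is √[(1 − q)(65² + m²) − ((1 − q)m)²] for m = 72 and 108. Totals and power are t-based, for a fixed design.

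| q | Difference | Total for 80% power | Power with 160 |
|---|---|---|---|
| 0 | 36.0 | 106 | 94% |
| 3.5% (half of NEC by day 14) | 34.7 | 116 | 91% |
| 7% (all NEC) | 33.5 | 128 | 88% |
| 14.5% (NEC, plus deaths at half of the 15%) | 30.8 | 158 | 81% |
| 22% (NEC, plus deaths at all of the 15%) | 28.1 | 192 | 73% |

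The two tables read the pilot mean differently: as all-randomized in the first and event-free in the second. The protocol says only that 40 infants "had a mean enteral intake at 14 days of 72 mL/kg/d", so either reading is an assumption.

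**The case against.** The plan states an intent-to-treat aim, speaks of the two randomized groups, and will test time to withdrawal. These help but do not close the gap. The aim is hedged and followed at once by an allowance for lost infants, the phrase names the arms rather than the analysis set, and the logrank test can reveal unequal withdrawal without placing anyone in P1.1.

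The stronger objection concerns size. The 10% versus 4% split has no source in the documents, the inflation is small even so, and it depends on which null is chosen. That stands. A reader might infer from the 7.0% that the trial is likely to claim a false benefit. The documents do not support this. If Group 1 loses more infants, as the expectation about bleeding would suggest, most of those rejections run against omission and the practical effect is lost power. The opposite imbalance is also possible.

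A reader might also infer that stool and calprotectin data are certainly lost. The plan never says that collection stops, and the S2.1 fraction of positive stools can be computed from stools before the event.

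Finally, making the all-randomized analysis primary is a choice of estimand. It is, however, the one nearest to the plan's own stated aim.

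**Conclusion.** The gap is real and should be fixed. The plan withdraws infants for post-randomization events, implies without saying so outright that they are not evaluable, and gives no rule for P1.1 at either look. Confidence is high on the missing rule and low on the size of any bias. Under the assumed 10% versus 4% loss and equal all-randomized means, the shift is 2.2 to 5.0 mL/kg/d. It is zero with equal loss and equal intake, or when event-free infants have equal means in both arms. Neither a definite bias nor its direction can be read from the documents.

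The figures apply to intake at day 14, the time point of the power calculation. Statistical Analysis names total weekly intake instead. That mismatch must be reconciled as a separate issue. It matters here only because it decides whether an infant withdrawn after day 14 already has a P1.1 value.

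**What to change.** Leave the trigger list and the clinical handling as they are, and change the data and analysis rules:

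1. State that a trigger event does not end data collection, and continue chart abstraction to day 42.
2. Define evaluable. Analyse P1.1 at the interim and final looks in all randomized infants by assigned group, using recorded intake including zero, with the evaluable-only analysis as sensitivity.
3. Pre-specify how deaths before the measurement enter P1.1, with a sensitivity analysis. The method is the sponsor's choice.
4. Report NEC, perforation, gross bleeding and death by arm, with risk differences and 95% confidence intervals.
5. Restate power for the chosen set.

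The cost is a little more abstraction, since intake already comes from the charts, and a possibly smaller expected effect. With 3.5% to 7% of each arm at zero intake, 160 infants still give about 91% to 88% power before interim adjustment. Scoring deaths as zero as well would lower this, to about 73% if the whole 15% are deaths.

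### The stated worst-case average of 89 evaluable needs a futility stop that the plan rules out (as written it is about 119), and no final critical value is given for P1.1; a 5% cut-off there would give about 6.2% type I error

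*Combined protocol and SAP*

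**What the plan says.** Sample Size Determination / Power Analysis starts from a fixed design: "we would require 104 evaluable subjects in a non-sequential design for Primary 1.1 to achieve 80% power at" the two-sided 5% level. It then adds one interim look at 66 evaluable infants, using a cited minimax two-stage method. The rules at that look are:

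- |Z|>2.28: stop for significance.
- |Z|<1.12: review for possible futility.
- Then: "There will be no stopping for futility. Otherwise, the study will accrue 120 evaluable subjects (54 more").

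The next sentence claims: "No competing two stage design can achieve a lower worst case scenario average sample size than this one's 89 evaluable".

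Statistical Analysis names a two-sided Welch t-test for P1.1 and, for the interim, says only: "An interim analysis of P1.1 will also be done as described in the Power Analysis section below". On thresholds it says: "For descriptive purposes, a P-value of under 5% will be declared significant". On intervals it says that "each hypothesis will be accompanied by a point estimate and 95% confidence interval estimate for effect size". Neither sentence exempts P1.1. Neither section gives a critical value for the look at 120.

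**The concern.** There are two linked problems.

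First, the average sample size belongs to a different design. A worst-case average of 89 out of a maximum of 120 requires the trial to stop often at 66, including when the interim result is weak. The plan removes that kind of stop but keeps the figure.

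Second, the decision rule for the only powered hypothesis is incomplete. The interim look uses part of the 5%, so the final look cannot also be judged at an unadjusted 5%. The Statistical Analysis section refers the reader to the power section, which stops at the 2.28 rule. If the final cut-off came from a design with a binding futility stop, it would rely on trials that stop at |Z|<1.12 never being able to reject later. Once those trials continue, that cut-off no longer holds 5%.

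At stake is how a final P1.1 result between about P=0.037 and P=0.05 would be read. Unless this is settled before the final data are seen, the choice of threshold could depend on the result.

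**Working it through.** **Inputs, all from the power section.** Control mean 72 and target 108 mL/kg/d, so the difference is 36; SD 65; two-sided 5%; 80% power; looks at 66 and 120 evaluable; interim bounds 2.28 and 1.12. Equal allocation is taken from the Randomization section.

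**Fixed design.** n per arm = 2 × (1.960 + 0.842)² × (65/36)² = 51.2, rounded up to 52, so N = 104. This reproduces the plan's figure.

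**Average sample size.** E[N] = 66 + 54 × P(continue). The interim Z has mean (δ/65) × √66/2, which is 2.25 at δ = 36.

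| Rule at 66 | P(continue) | E[N] |
|---|---|---|
| Binding stop at \|Z\|<1.12, worst case (δ about 27 mL/kg/d) | 0.4405 | 66 + 54 × 0.4405 = 89.8 |
| As written, worst case (δ = 0) | 1 − 0.0226 = 0.9774 | 66 + 54 × 0.9774 = 118.8 |
| As written, δ = 36 | 1 − 0.488 = 0.512 | 66 + 54 × 0.512 = 93.7 |

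The stated 89 therefore matches the binding design to within 1 infant, and understates the worst case of the written design by about 30.

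**Optimality claim, for the design as written.** Keep the same first look (66, |Z|>2.28, no futility stop), but use a maximum of 108 and a final |Z|>2.072. This gives 5.0% type I error, 80.2% power and a worst case of 66 + 42 × 0.9774 = 107.1, which is below 118.8.

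**Type I error.** The two Z statistics are treated as bivariate normal with correlation √(66/120) = 0.742. The overall error is P(|Z₁|>2.28) + P(trial continues and |Z₂|>c). The first term is 0.0226, leaving 0.0274 for the final look.

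| Final c | Type I error, no futility stop | Power at δ = 36, no futility stop | Type I error, binding 1.12 stop |
|---|---|---|---|
| 1.96 | 0.0226 + 0.0390 = 0.0616 | 86.5% | 0.0518 |
| 1.987 | 0.0589 | 86.0% | 0.0500 |
| 2.088 | 0.0500 | 83.9% | not needed |
| 2.28 | 0.0381 | 79.4% | 0.0353 |

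The value 1.987 is inferred: it is what holds 5% under a binding 1.12 stop (with 80.6% power). The plan does not state it. Of the excess at 1.96, 0.0616 − 0.0518 = 0.0098, about 1.0 percentage point, comes from dropping the futility stop.

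**Check with the planned test.** In 400,000 simulated trials with Welch t-tests (33 then 60 per arm, interim nominal P<0.0226), the type I error was 0.0614 at a final P<0.05 and 0.0499 at P<0.0368. Power at P<0.0368 was 83.1%. A separate simulation that applied 2.28 directly to the interim t statistic gave 0.0639 at a final P<0.05.

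**Timing of the interim look.** With the interim bound at 2.28 and a maximum of 120, the final nominal P that holds 5% is 0.0357 for a look at 60, 0.0368 at 66 and 0.0380 at 72.

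**The case against.** The strongest reply is that the 6.2% is a scenario. Nowhere does the plan say that P1.1 will be judged at |Z|>1.96 at the final look. The 5% rule is introduced as descriptive and covers all hypotheses, and the cited minimax method may fix a final value that the documents do not print. Silence is also compatible with reusing 2.28, which would give 3.8% type I error and 79.4% power. This stands as a limit on the 6.2%, which is conditional. It does not remove the gap: if the 5% rule does not govern P1.1, the final look has no stated rule at all. And if the cited method's value was set for a binding 1.12 stop, it would give about 5.9% here.

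A second reply is that the average sample size drives no analysis. That is fair. The maximum, the planned accrual and the power do not suffer, and at the design effect the gap is only about 5 infants (93.7 against 89). Taken alone, this would be a correction of wording.

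Third, the 66/108 design does not beat 89, so it does not refute the optimality claim for a design with binding futility. That is correct. It shows only that the claim fails for the design as written.

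**Conclusion.** The concern holds on both parts. The worst-case average of 89 and the optimality sentence describe a design with a binding futility stop, which the plan excludes. As written, the worst case is 118.8 evaluable, at the null. No final critical value for P1.1 is stated. Applying the general P<5% rule gives an overall two-sided type I error of 6.16%, against the 5% designed for; |Z|>2.088 (nominal P<0.0368) holds 5%.

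These results assume looks at exactly 66 and 120 evaluable, equal allocation and approximately normal test statistics. The power figures also assume a difference of 36 and SD 65. The 2.28 interim boundary can stand, and dropping the futility stop does not reduce power. The missing final rule makes this a must-fix, because it decides the only powered hypothesis.

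**What to change.** Keep the 2.28 boundary at 66 and the decision not to stop for futility, and make these changes:

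1. In the power section, add: At the final analysis P1.1 is significant only if the two-sided nominal Welch P is below 0.0368 (|Z|>2.09); this value will be recomputed if the interim look is not at exactly 66 of 120 evaluable.
2. In Statistical Analysis, exempt P1.1 from the general 5% rule and report its final interval at the matching level, 1 − 0.0368, or about 96.3%. It would help also to state the level if the trial stops at the interim; the match to 2.28 is 1 − 0.0226, or about 97.7%.
3. Replace the sentence on 89 evaluable by: The worst-case average is about 119 evaluable, and about 94 under the alternative. Delete the claim that no competing design does better.

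Reinstating a binding stop at |Z|<1.12 would also reconcile the text, but it changes the design and would still need a stated final value (about 1.987, with 80.6% power).

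The recommended change costs no infants. The final threshold becomes slightly stricter and the quoted average sample size less favourable. Power at 120 evaluable stays at about 83–84%, above the 80% target.
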